12.1. Adverse Event Relationship Terms

All Adverse Events (AEs) occurring in this study will be reported, including characterization by severity, seriousness and relatedness, as described below. Investigators will record characteristics of each adverse event on an Adverse Event CRF. Each adverse event will be judged by the Investigator as to its relationship to the investigational device. In addition, the Investigator will identify the date of onset, severity, seriousness, relatedness and duration of the AE. Severity will be judged using the scale noted in *Table 12.1.1: Definition of event severity for judgment by Investigator*. Seriousness will be judged using the criteria listed in *Table 12.1.2: Definition of serious adverse event, adapted from 21 CFR 803.3*. Device relatedness will be determined by the criteria listed in *Table 12.1.3: Definition of event relatedness*. All adverse events will be monitored until they are adequately resolved, explained or the subject has exited the study.

Table 12.1.1: Definition of event severity for judgment by Investigator.

| Definition of event severity for judgment by Investigator. | |
|--|---|
| Term | Definition |
| Mild | Subject is aware of a sign or symptom, but that sign or symptom does not interfere with normal activity OR symptom is both transient and resolved without treatment |
| Moderate | Symptoms interfere with the subject’s usual activity OR symptoms require treatment |
| Severe | Symptom(s) cause either severe discomfort OR have a significant impact of the subject’s usual activity and symptoms require treatment |

Table 12.1.2: Definition of serious adverse event, adapted from 21 CFR 803.3.

| Definition of serious adverse event, adapted from 21 CFR 803.3. |
|--|
| An event is considered serious if it: 
 (1) Is life-threatening, (2) Results in permanent impairment of a body function or permanent damage to a body structure, or (3) Necessitates medical or surgical intervention to preclude permanent impairment of a body function or permanent damage to a body structure. 
Permanent means irreversible impairment or damage to a body structure or
 |

| |
|---|
| function, excluding trivial impairment or damage. |
|---|

Table 12.1.3: Definition of event relatedness

| Definition of event relatedness | |
|---------------------------------|--|
| Term | Definition |
| Definite | Adverse event whose timing is highly plausible for causality and which cannot be explained by other factors |
| Probable | Adverse event whose timing is reasonable for causality and is unlikely to be explained by other factors |
| Possible | Adverse event whose timing is reasonable for causality but which could be explained by other factors |
| Not related | Adverse event whose timing makes causality improbable and which could easily be explained by other factors |
| Unknown | Adverse event whose plausibility of timing cannot be judged or in which information regarding other factors does not exist |

12.2. Reporting Requirements

The communication requirements for Adverse Events reporting, from the beginning of enrollment through procedure completion, to Ottobock are as follows in *Table 12.2.1: Adverse Event Reporting Requirements* below:

Table 12.2.1: Adverse Event Reporting Requirements

| Adverse Event Reporting Requirements | | | |
|--------------------------------------|--|--|--|
| Adverse Event Classification | Methods of Communicating Events to Ottobock | Communication Timeline to Ottobock | Source Documentation Requirements |
| SAE and/or SADE | Complete AE CRF with all available information. If CRF is unavailable, fax information to the Ottobock Clinical Affairs Department. | Within 24 hours of first becoming aware of the event | Provide copies of all relevant source documents requested by Ottobock or designee as soon as possible after reporting the event. |
| AE/ADE | Complete AE CRF | Review with Monitor during next monitoring visit | No source documents are required to be submitted to Ottobock. |

Table 12.2.2: Sponsor and BionX Reports

| Sponsor and BionX Reports | | | |
|---------------------------|---|-----------|---|
| Responsible Party | Report | Submit to | Description |
| Sponsor | SADE, Device-related AEs | BionX | All SADEs will be sent to BionX Regulatory Affairs within 24 hours of first becoming aware of the event for review for possible Medical Device Reporting (MDR) in accordance with 21 CFR 803.20. All device-related AEs will be sent to BionX Regulatory Affairs department in a monthly report for MDR assessment. |
| BionX | Death or serious injury; device malfunction | FDA | Notification within 5 workdays, 10 workdays or 30 calendar days after BionX first learns of the event in accordance with 21 CFR 803.20, depending on the source and action required. |

12.3. *Device deficiencies, Device failures, Malfunctions, and Product Nonconformities*

All product deficiencies related to the identity, quality, durability, reliability, safety or performance of the medical device, failures, malfunctions and product nonconformities will be documented on the appropriate CRF and immediately reported to the sponsor (without any delay that cannot be justified and within 24 hours of occurrence). In such cases, the product should either be returned to BionX (an Ottobock company, located at [name]) for analysis or a BionX employee will either inspect or service at the center. Instructions for returning the product will be provided to the centers. Product failures and malfunctions should also be documented in the subject’s medical record.

NOTE: Product failures, malfunctions, and product nonconformities are NOT to be reported as adverse events. However, if there is an adverse event that results from an product failure or malfunction, that specific event should be recorded on the AE CRF.

12.4. *Reporting to Regulatory Authorities /IRBs /ECs /Investigators*

Ottobock is responsible for reporting adverse event information to all participating investigators and regulatory authorities as applicable. The Site Principal Investigator is responsible for informing the IRB of SAEs or other events as required by the overseeing IRB. A copy of any reports to IRBs should be sent to the Ottobock Clinical Operations and BionX Regulatory Affairs Department.

13. Risk Benefit Analysis

The emPOWER Ankle prosthesis is designed to provide bionic propulsion, emulating the biological function of an ankle, and attaches to the wearer by a previously fit socket. The benefits of bionic propulsion for the amputee (as compared to conventional prostheses) have been studied and published in peer-reviewed scientific journals, summarized as follows:

- a) walk with a more natural gait;

- b) reduce musculoskeletal stress believed to be causal of osteoarthritis;
- c) use less energy to walk;
- d) walk at a normal preferred speed;
- e) navigate uneven terrain with less effort and greater speed.

The device's safety and performance profile has been assessed and has been found to add no additional risk to the typical lower-limb prosthetic ankle device.

13.1. *Known and Anticipated Risks*

The emPOWER Ankle is not expected to produce any additional or unique risks as compared to those already associated with existing lower-limb prostheses. The anticipated risks are summarized as:

1. Trip / Fall Hazard: The risk of trips/falls is inherent to the lower-extremity amputee population based on the nature of the condition. The emPOWER Ankle device, by emulating normal biological function of the ankle, is anticipated to exhibit a lower incidence of trips/falls than conventional (non-microprocessor) ankle prostheses.
2. Fire Hazard: The risk of fire from the Li-ion battery which powers the emPOWER Ankle is minimized through design, control circuitry and compliance/testing to international standards.
3. Electrocution Hazard: The battery-powered ankle prosthetic itself does not present a risk of electrocution, however the AC-powered battery charger presents the same risk of electrocution as other 120V AC powered devices.

13.2. *Risk Minimization*

The Sponsor will employ measures throughout the course of this study to minimize risks to subjects choosing to participate. All efforts will be made to minimize potential risks by:

1. Selecting Principal Investigators who are experienced and skilled in fitting and aligning lower limb prostheses.
2. Providing training on the equipment prior to use
3. Defining inclusion/exclusion criteria clearly to ensure only appropriate subjects are enrolled.
4. Ensuring that the treatment of the subject is consistent with current medical practices.

14. Subject Benefit

Subjects who demonstrate improvements using the emPOWER Ankle compared to their passive prosthetic device will be offered the opportunity to continue using the emPOWER Ankle at the end of the study until there is Medicare payment available for the subject to purchase a emPOWER Ankle. The subject will not be told of this prior to study completion to avoid bias. All subjects will receive fair compensation for completion of the study to cover costs of travel to and from the study center and for any potential lost wages due to the study visits.

15. Ethical Considerations

15.1. *Study Conduct*

The Investigator will conduct the study within the regulations and guidelines of the Food and Drug Administration (FDA) and all country/state/local regulations, whichever affords the greater protection to the subject.

15.2. *Institutional Review Board*

A copy of the protocol, proposed ICF, other written subject information and any proposed subject recruitment material must be submitted to the IRB for written approval prior to use. A copy of the written IRB approval of both the protocol and ICF, as well as the IRB's concurrence with the justification for non-significant risk status, must be received by Ottobock before recruitment of subjects into the study and shipment of product.

The Investigator must submit and, where necessary, obtain approval from the IRB for all subsequent protocol amendments and changes to the Informed Consent form. The Investigator must notify the IRB of deviations from the protocol and SAEs occurring at the site and other SAE reports received from Ottobock in accordance with the overseeing IRB's requirements.

The Investigator is responsible for obtaining annual IRB approval and renewal throughout the duration of the study. Copies of the Investigator's reports and the IRB continuance of approval must be sent to Ottobock.

15.3. *Informed Consent Form*

Ottobock will provide a sample ICF to the Investigator to prepare for use at his/her site. The written Informed Consent documents should be prepared in the language(s) of the potential subject population.

Ottobock and the reviewing IRB must approve the ICF before use at that center. The ICF(s) must be in agreement with the 21 CFR Part 50.

15.4. *Obtaining Informed Consent*

The background of the proposed study and the benefits and risks of the procedures and study must be explained to the subject. The subject must sign the consent form prior to enrollment. This form or a modification based on IRB recommendations must be presented to and signed by all enrolled subjects and signed by the principal investigator or designee.

Prior to obtaining informed consent, information should be given in a language and at a level of complexity understandable to the subject in both oral and written form by the investigator or assigned designee. Subjects should not be coerced, persuaded, or unduly influenced to participate or remain in the study. A subject or his/her legal representative must be given ample time and opportunity to inquire about details of the study and all questions about the study should be answered to the satisfaction of the subject or the representative.

Prior to participation in the study, the written informed consent form should be signed and personally dated by the subject or his/her legal representative, and by the person who conducted the informed consent discussion (investigator or designee). If the subject or his/her legal representative is unable to read the consent form, a witness will need to be present during the entire informed consent discussion. After the informed consent form is read to the subject and signed by the subject or his/her legal representative, the witness should also sign the consent form, attesting that informed consent was freely given by the subject. The informed consent process should be documented in each subject's record.

The subject or his/her legal representative must receive a copy of the signed and dated informed consent form.

The consent form should be updated or amended whenever new information becomes available that may be relevant to the subject.

Subjects will be informed that the sponsor and regulatory authorities will have access to personally identifying information for the purposes of monitoring data against source documentation. However, all data stored and presented by the sponsor will be in anonymous form.

15.5. *Amending the Protocol*

This protocol must be followed exactly, and can be altered only by written amendments by the study sponsor.

15.6. *Emergency Actions*

Ottobock accepts the right of the Investigator to deviate from the protocol only in an emergency when necessary to safeguard the life or the physical well-being of a study subject. The Investigator must give notice of any emergency deviations and justification for the deviation to Ottobock and the IRB as quickly as possible after the episode, but in any event no later than 24 hours after the emergency.

15.7. *Protocol Adherence*

Prior to beginning the study, the Investigator must sign the Investigator Agreement and Protocol Signature page documenting his/her agreement to conduct the study in accordance with the protocol. An Investigator must not make any changes or deviate from this protocol, except to protect the life and physical well-being of a subject in an emergency. Each deviation from the protocol must be documented with the date and reason for the deviation and reported to Ottobock and to the IRB, per local guidelines and government regulations.

16. Study Logistics

Ottobock and BionX will make necessary efforts to ensure that this study is conducted in compliance with Good Clinical Practices and all applicable regulatory requirements.

All personnel to participate in the conduct of this clinical study will be qualified by training, education and/or experience to perform his or her respective tasks.

16.1. *Data Management*

Subject data will be collected on case report forms (CRFs). The Principal Investigator or Sub-investigator must ensure the accuracy and completeness of the recorded data. Changes to data previously submitted to the sponsor will require the Investigator to acknowledge/approve the changes in writing.

Visual and/or computer data review will be performed to identify possible data discrepancies. queries will be created and will be issued to the center for appropriate response. The site staff will be responsible for resolving all queries.

Data from all study subjects through point of study completion or study withdrawal will be reported.

16.2. *Monitoring and Auditing*

Monitoring visits to the centers will be made periodically during the study, to ensure that all aspects of the current, approved protocol/amendment(s) are followed. Original source documents will be reviewed for verification of data. The Investigator/institution guarantees direct access to original source documents by Ottobock personnel, their designees, and appropriate regulatory authorities. In the event that the original medical records cannot be obtained for a subject that is seen by a non-study physician at a non-study institution, photocopies of the original source documents must be made available for review.

The study may also be subject to a quality assurance audit by Ottobock and/or BionX or its designees, as well as inspection by appropriate regulatory authorities.

It is important that the Investigator and relevant study personnel are available during the monitoring visits and audits and that sufficient time is devoted to the process.

16.3. *Device Accountability*

Device accountability records must be maintained at each center. The quantity of devices received by each center, those returned to the supplier, and those devices used at the center will be recorded in the device accountability record. The Investigator must explain in writing the reasons for any discrepancy noted in device accountability. The centers will return any emPOWER product unwanted by subjects back to BionX. BionX will provide instructions to the centers on the proper method to return the used product.

16.4. *Record Retention*

The Investigator will maintain all essential study documents and source documentation, in original format, that support the data collected on the study subjects. Documents must be retained for at least 2 years after clearance of the marketing application or until at least 2 years

have elapsed since the formal discontinuation of the clinical investigation of the product, whichever is later. When these documents no longer need to be maintained, it is Ottobock's responsibility to inform the Investigator. The Investigator will take measures to ensure that these essential documents are not accidentally damaged or destroyed. If for any reason the Investigator withdraws responsibility for maintaining these essential documents, custody must be transferred to an individual who will assume responsibility. Ottobock must receive written notification of this custodial change.

16.5. ***Criteria for Terminating Study***

Ottobock reserves the right to terminate the study but intends only to exercise this right for valid scientific or administrative reasons and reasons related to protection of subjects. Investigators and associated IRBs will be notified in writing in the event of termination.

16.6. ***Criteria for Suspending/Terminating a Study Center***

Otto Bock HealthCare LP reserves the right to either suspend or terminate enrollment at a study center at any time after the study initiation if no subjects have been enrolled, if the center has multiple or severe protocol deviations or violations without justification or fails to follow remedial actions.

16.7. ***Insurance***

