9.1. Screening

Subjects presenting to Investigators with transtibial amputations and who are currently using a passive prosthetic device will undergo evaluation for potential participation in the study.

A subject will sign the study-specific informed consent form (ICF) prior to performing any test involved in determining eligibility that goes beyond standard of care.

Each subject must meet the inclusion/exclusion criteria for this study to be eligible for study participation.

9.2. *Moment of Enrollment*

Subjects will be considered “enrolled” in the study once compliance with all inclusion and exclusion criteria has been verified and documented; and the subject has signed the informed consent form. At that point, the subject will enter the baseline phase of the study.

9.3. *Subject Identification*

Each subject will be assigned a unique subject identification number at the time of consent. This subject identification number will be retained throughout the study if the subject is enrolled. Sites will keep a log that notes the subject’s name and corresponding subject identification number. All case report forms (CRFs) will be tracked, evaluated, and stored using only the subject ID number and initials. No personal other identifying information will be included on the CRFs.

The ICF will notify subjects that study monitors, auditors, and representatives of government agencies will have access to personal identifying information to ensure that data reported on the CRFs corresponds to the person who signed the ICF and the information contained in the source documentation.

9.4. *Phase I: 1st Visit - Baseline*

For each of the enrolled subjects, characteristics at the time of the procedure including: age, sex, weight, amputation side(s) and amputation type(s), medical history will be recorded. At day of enrollment, subjects will complete:

- Amputee Mobility Predictor (AMP)
- Physical Assessment
- Fitted with a Fitbit® One™ activity tracker
 - The activity tracker will to be used to monitor steps taken on their passive prosthetic device for 14 days. A minimum of twenty-seven hundred (2700) recorded daily steps while using the passive prosthesis will be documented toward ability to perform the study’s 6MWT. [12]
- Subjects will be provided a patient diary to track activity, falls and self-reporting of activities of daily living.

9.5. *Phase I: 2nd Visit - Study Procedure*

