At the second visit, the subject will complete the following study assessments wearing the passive prosthetic:

- 6MWT
- Ramp Ascent
- Ramp Descent
- ABC Scale
- Falls Efficacy Scale
- Mobility PLUS-M (12 item Short Form)
- PROMIS Questionnaires

At the end of the second visit, subjects will be fitted with the emPOWER Ankle by a qualified clinical prosthetist, trained by BionX personnel. This fitting includes selection of the appropriate size and category carbon fiber foot, alignment, and tuning in accordance with the emPOWER Instructions For Use (IFU). The prosthetist will make a determination that the tuning was successful (within the bounds specified by the IFU) and the Investigator will maintain a copy of the Tuning Record. This initial Tuning Record may also be used to verify that the subject has the ability to walk at a self-selected walking speed (SSWS) > 0.75 meters per second with the current prosthesis and can walk with variable cadence, where variable cadence is defined as three distinguishable walking speeds with a minimum SSWS of 0.75 m/s (one below SSWS, and one above SSWS) on the Tuning record. Distinguishable will be defined as no overlap between the three (3) primary step groupings for each walking speed displayed on the Tuning Record.

At fitting of the emPOWER Ankle, the Investigator will instruct the subject to utilize the device for a 16-day period of time, within the intended and foreseeable range of use (e.g. – ramps, stairs, limited running or jumping, stepping sideways, etc.). In addition, the investigator will take the subject through a series of default operating conditions of the emPOWER Ankle in the clinic setting such as with the power turned off.

Each subject will take the emPOWER Ankle (including batteries and charger) home for 16 days (to ensure 14 full days of step counts) of use in everyday life situations. The subject will not be under the observation of the Investigator during this take home period. During the at home portion of the study, subjects will continue to monitor daily steps with use of a Fitbit® One™ during the time that they are wearing the emPOWER Ankle. Subjects will also maintain an Activities of Daily Living Diary during the take home evaluation portion of the study. This Diary will allow subjects to note specific activity changes due to the emPOWER Ankle and serve as a log for recording any falls.

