9.8. Phase II: 5th Visit – Crossover Visit

Subjects will be seen by the prosthetist after wearing their passive prosthetic foot for 2-4 weeks. The window for this visit is 2-6 weeks after passive device fitting.

For a minimum of 14 days prior to this visit, the subject should wear the Fitbit and complete the patient diary for steps, falls and daily activity.

During this visit, the subject will complete the following study assessments wearing the passive prosthetic:

- 12MWT (with distance walked assessed at 6 and 12 minutes)
- 10MWT
- L-Test
- Ramp Ascent
- Ramp Descent
- ABC Scale
- Falls Efficacy Scale
- AMP
- Mobility PLUS-M (12 item Short Form)
- PROMIS Questionnaires
- PSFS
- NPRS

At the end of the study visit, subjects will return to wearing the emPOWER Ankle for the remainder of the study. If there are any adjustments to the tuning settings different from those previously used for the emPOWER Ankle, the tuning record should be saved.

9.9. ***Phase II: 6th Visit – 6 Month Visit***

Subjects will be seen by the prosthetist. The window for this visit is -4 weeks / + 3 months.

During this visit, the subject will complete the following study assessments wearing the emPOWER Ankle:

- 12MWT (with distance walked assessed at 6 and 12 minutes)
- 10MWT
- L-Test
- Ramp Ascent
- Ramp Descent
- ABC Scale
- Falls Efficacy Scale
- AMP
- Mobility PLUS-M (12 item Short Form)
- PROMIS Questionnaires
- PSFS
- NPRS

If there are any adjustments to the tuning settings for the emPOWER Ankle, the tuning record should be saved.

9.10. ***Phase II: 7th Visit – 12 Month Visit (Final Study Visit)***

Subjects will be seen by the prosthetist. The window for this visit is -3 months / + 3 months. This will be the final study visit.

During this visit, the subject will complete the following study assessments wearing the emPOWER Ankle:

- 12MWT (with distance walked assessed at 6 and 12 minutes)
- 10MWT
- L-Test
- Ramp Ascent
- Ramp Descent
- ABC Scale
- Falls Efficacy Scale
- AMP
- Mobility PLUS-M (12 item Short Form)
- PROMIS Questionnaires
- PSFS
- NPRS

9.11. **Table 9.11.1: Procedures and Assessments**

The following table summarizes the timing and specific assessments to be conducted in this study:

| ASSESSMENT | BASELINE 1ST Visit | PASSIVE DEVICE ASSESSMENT/ ANKLE FITTING 2nd Visit | emPOWER Follow-Up 3rd Visit | 3 MONTHS 4th Visit | CROSSOVER 5th Visit | 6 MONTHS 6th Visit | 12 MONTHS 7^h Visit |

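### Section 12.2 ends the 24-hour SAE/SADE reporting window at an undefined procedure completion, which conflicts with adverse-event collection to study exit in 12.1 and Table 9.11.1

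*Combined protocol and SAP*

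**What the plan says.** Section 12.2 opens with "The communication requirements for Adverse Events reporting, from the beginning of enrollment through procedure completion, to Ottobock are as follows", followed by Table 12.2.1. For SAEs and SADEs the table sets the deadline "Within 24 hours of first becoming aware of the event"; other AEs and ADEs wait for the next monitoring visit. No section defines procedure completion.

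The word appears in one visit title, that of section 9.5: "Phase I: 2nd Visit - Study Procedure". At that visit the passive-device tests come first, and then "At the end of the second visit, subjects will be fitted with the emPOWER Ankle by a qualified clinical prosthetist". The same section goes on to the home period: "Each subject will take the emPOWER Ankle (including batteries and charger) home for 16 days", and "The subject will not be under the observation of the Investigator during this take home period". Subjects who continue wear the device to the 3-month visit. After the passive re-accommodation period, section 9.8 says "subjects will return to wearing the emPOWER Ankle for the remainder of the study".

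Section 12.1 has no such cut-off. It requires every adverse event in the study to be reported on an AE CRF and adds "All adverse events will be monitored until they are adequately resolved, explained or the subject has exited the study". Table 9.11.1 marks adverse events at Visits 1, 2, 3, 5, 6 and 7.

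**The concern.** The limit in 12.2 would suit a one-time intervention, but this device is worn for up to about a year. If a site ties procedure completion to the visit that bears the name, its stated 24-hour duty to the sponsor ends as device exposure begins or shortly after.

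Section 13.1 lists trips and falls first among the anticipated risks, and much of the wear is at home, away from the investigator. What is at stake is how quickly the sponsor hears of a serious event. Under Table 12.2.2 the sponsor forwards SADEs to BionX within 24 hours of becoming aware, for possible Medical Device Reporting, so a slow report from the site can delay that step too.

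**Working it through.** The protocol gives no figure to reproduce. The check compares the passages and then sizes the wear left outside the window under each reading.

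**Step 1: what procedure completion could mean.**
- The title of section 9.5 points to Visit 2.
- Section 9.5 also contains the 16-day home period, so the end of that period is a second reading under the same title.
- Section 5 speaks of study procedures for the emPOWER, which come after fitting and could extend to the 3-month testing.
- Table 9.11.1 has procedures in its title and spans all seven visits, so completion could mean Visit 7.
- Section 9.4 uses the procedure for the baseline visit, which shows that the word has no fixed meaning.

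**Step 2: inputs for the size.** Assumptions: 12 months is 365 days and 3 months is 91 days, both counted from fitting. The passive period is 2 weeks at the least (section 9.8) and 6 weeks at the most (the Visit 5 window), that is 14 to 42 days. Visit 3 falls 16 days after Visit 2, with a window of +1 week, so day 16 to 23.

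emPOWER wear to 12 months = 365 − passive days: 365 − 14 = 351 days, or 365 − 42 = 323 days.

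**Step 3: share of wear inside the 12.2 window** = wear days up to the end point / total wear days.

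| Reading of the end point | Calculation | Share covered |
|---|---|---|
| Visit 2 (fitting) | 0/351 to 0/323 | 0% |
| End of the 16-day home period | 16/351 to 16/323 | 4.6% to 5.0% |
| Visit 3 at its latest | 23/351 to 23/323 | 6.6% to 7.1% |
| 3-month visit (nominal) | 91/351 to 91/323 | 25.9% to 28.2% |
| Visit 7 | all/all | 100% |

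**Step 4: sensitivity.** The 12-month visit has a window of ±3 months. At its earliest, with the longest passive period, wear is 365 − 91 − 42 = 232 days, and 23/232 = 9.9%. So for a subject who completes Phase II, either reading under the 9.5 title leaves at least 90% of wear outside. A subject who stops at Visit 3 has most or all wear covered on the 16-day reading, and none on the Visit 2 reading.

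**Step 5: do other passages supply the missing deadline?**

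| Passage | What it requires | 24-hour site-to-sponsor rule for an AE? |
|---|---|---|
| 12.1 | Report all AEs; monitor to resolution, explanation or exit | No deadline |
| 10.13 | Diary-found AEs go on the AE form | No deadline |
| Table 9.11.1 | AEs at four of the five visits after Visit 2 | No deadline |
| 12.3 | Deficiencies, failures and malfunctions to the sponsor within 24 hours of occurrence | Yes, but for device faults only |
| 12.4 | Investigator informs the IRB of SAEs as the IRB requires; copies to Ottobock and BionX | Timing left to the IRB |

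A serious event without malfunction, occurring after the 12.2 window closes, has no stated 24-hour route to the sponsor.

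**The case against.** The best defence is that Visit 2 is only one reading. The protocol uses procedure loosely, and taking procedure completion as the end of everything listed in Table 9.11.1 is natural and agrees with 12.1. A careful site may well send 24-hour reports throughout. This stands in part: the documents establish an ambiguity, not a fixed cut-off at Visit 2. It does not remove the problem, because 12.2 does not state the Visit 7 reading and a site can defend an earlier one from the heading of 9.5.

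A reader might also infer that adverse events during device wear would go uncounted. The documents do not support that. Table 12.2.1 governs how and when events reach the sponsor. Recording rests on 12.1, 10.13 and the visit schedule, and 16.1 reports data from all subjects to completion or withdrawal.

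Nor is every route to the sponsor or BionX cut. Section 12.3 covers faults, where a battery fire or charger fault would ordinarily fall, and 12.4 sends copies of IRB reports to both companies. These routes narrow the gap to serious events without malfunction, where timing then depends on the IRB's own rules.

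Finally, the percentages count days of wear, not expected events, and they apply to subjects who choose to enter Phase II. Both limits are fair.

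**Conclusion.** Wrong as written: 12.2 contradicts 12.1 and Table 9.11.1 on how long safety reporting runs. Severity is moderate.

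On either reading under the Study Procedure title, 0% to about 5% of emPOWER wear to a nominal 12 months falls inside the 24-hour window (up to about 7% if it is stretched to a late Visit 3). Only a reading to the final visit covers all of it. This rests on 365 days of follow-up from fitting, 14 to 42 passive days, and a subject who continues through Phase II.

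The consequence is possible delay in expedited reports of serious events without malfunction. The stronger conclusion, that 24-hour reporting definitely stops on the day the device goes home, goes beyond the text: the term is undefined, and 9.5 itself runs through the 16-day home period. Safety counts and the 6MWT comparison are untouched.

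**What to change.** Reconcile the passages by changing the end point in 12.2: in place of procedure completion, state that the requirements apply until the subject has exited the study. This matches the follow-up limit in 12.1 and the adverse-event entry at Visit 7 in Table 9.11.1. The start, at the beginning of enrollment, can stay; moving it is not needed to resolve this contradiction.

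The cost is a one-sentence amendment and perhaps a few more expedited reports in at most ten subjects.
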